10.1 Sample Size

To achieve a power of 80%, with two-sided significance, and to detect a mean difference

in serum concentration of 2 mg/L difference a minimum sample size of 42 patients in each cohort would be required. Increasing the sample size beyond this point would achieve greater power to detect smaller differences in serum concentrations between subgroups.

10.2 Analysis

Descriptive statistics will be used to analyze baseline characteristics. The primary variable of interest will be golimumab drug levels. Other variables will include: efficacy, gender, age, smoking status, concomitant medication, disease location, disease duration, development of anti-drug antibodies, acute infusion reactions, serum CRP, albumin, fecal calprotectin, SCCAI, PRO2, IBD-Control.

Differences between responders and non-responders will be evaluated using a t-test with the threshold for statistical significance set at 0.05. Univariate and bi-variate analysis will be used to assess factors predicting response, including serum golimumab levels at each time point.

11 Direct Access to Source Data and Documents

The Investigator(s) will permit trial-related monitoring, audits, REC review, and regulatory inspections by providing the Sponsor(s), Regulators and REC direct access to source data and other documents (e.g. patients' case sheets, blood test reports, X-ray reports, histology reports etc.).

12 Ethics & Regulatory Approvals

The trial will be conducted in compliance with the principles of the Declaration of Helsinki (1996), the principles of GCP and in accordance with all applicable regulatory requirements including but not limited to the Research Governance Framework and the Medicines for Human Use (Clinical Trial) Regulations 2004, as amended in 2006 and any subsequent amendments.

This protocol and related documents will be submitted for review to the Research Ethics Committee (REC), and to the Medicines and Healthcare products Regulatory Agency (MHRA) for Clinical Trial Authorisation.

Subsequent protocol amendments will be submitted to the REC and Regulatory Authorities for approval, and that the Chief Investigator will comply with regulations, particularly specifying, Pharmacovigilance reporting and providing the REC & MHRA with progress reports, and a copy of the Final Study Report.

The Chief Investigator will submit a final report at conclusion of the trial to the KHP-CTO (on behalf of the Sponsor), the REC and the MHRA within the timelines defined in the Regulations.

13 Quality Assurance

Monitoring of this trial will be to ensure compliance with Good Clinical Practice and scientific integrity will be managed and oversight retained, by the KHP-CTO Quality Team.

14 Data Handling

The Chief Investigator will act as custodian for the trial data. The following guidelines will be strictly adhered to:

Patient data will be anonymised

 All trial data will be stored in line with the Medicines for Human Use (Clinical Trials) Amended Regulations 2006 and the Data Protection Act and archived in line with the Medicines for Human Use (Clinical Trials) Amended Regulations 2006 as defined in the Kings Health Partners Clinical Trials Office Archiving SOP.

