6.1 Inclusion Criteria

Adult patients with moderate-to-severe UC with an inadequate response to, or unable to tolerate, one or more of the following conventional therapies: oral 5-aminosalicylates, oral corticosteroids, immunomodulators; or are corticosteroid dependent.

Inclusion criteria for cohort 1:

- Aged 18 years or over
- Written informed consent to participate
- Moderate-to-severe UC, defined as:
 - SCCAI > 5 and,
 - i. A raised fecal calprotectin (> 59 µg/g) or,
 - ii. A raised CRP (> 5 mg/L) or,
 - iii. Endoscopic disease activity Mayo 2 or above,

Evaluated within 4 weeks of screening

- Commencing golimumab treatment
- Sufficient English language skills to understand the patient information sheet and consent form

Inclusion criteria for cohort 2:

- Aged 18 years or over
- Written informed consent to participate
- Receiving golimumab treatment for UC over 14 weeks (have completed 6 injections at time of screening)
- Sufficient English language skills to understand the patient information sheet and consent form

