7.1 By Visit

Cohort 1

Screening visit

- Signed Informed consent
- Review inclusion/exclusion criteria
- Demographic details: age, gender
- IBD-relevant concomitant medication review (Injection site reaction review is not applicable at this visit)
- Baseline clinical (SCCAI and PRO2) and biochemical assessments (CRP, albumin and FC)
- Baseline quality of life assessment (IBD-Control)
- UC disease related details: anatomic distribution (proctitis, left-sided disease or extensive colitis) and duration of disease

Day 0 (week 0), day 14 (week 2), day 42 (week 6), day 70 (weeks 10) and day 98 (week 14)

Patients self-administer golimumab at home.

Any late golimumab administrations (within a week of the planned injection date) would not be considered to significantly impact the integrity of the trial or its results and these will not be considered protocol deviations.

Day 38-42 (week 6), day 66-70 (week 10), day 94-98 (week 14)

- Serum golimumab concentration measurement
- Anti-golimumab antibody measurement
- Injection-site reactions and IBD-relevant concomitant medication review
- Clinical (SCCAI and PRO2) and biochemical assessments (CRP, albumin and FC)
- Quality of life assessment (IBD-Control)

In cohort 1 patients commencing induction therapy with golimumab, will receive delivery of the drug and self-injection training from registered nurses under the Homecare agreement already in place. This will be identical to the standard of care provided by the NHS (both at Guy's & St Thomas' and King's College Hospitals). Routine clinical care would usually involve clinical review prior to treatment initiation and again at approximately 10-14 weeks from treatment initiation. GO-LEVEL will include clinical and biochemical assessments made at weeks 6, 10 and 14, and one of these will be arranged to coincide with their routine clinical appointment. Taking part in the study will therefore involve an additional two visits for patients, above routine clinical care. Patients will be asked to self-administer their treatment in the usual way and visits will be arranged such that trough concentrations will be measured within four days *prior* to the subsequent dose. Golimumab injections could be given on the same day as the trial visit but assessments and blood tests must be taken *prior* to self-administration.

Cohort 2

Screening visit

- Signed Informed consent
- Review inclusion/exclusion criteria
- Demographic details: age, gender

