9.3 Treatment Stopping Rules

Because this is a non-interventional trial there won't be an interim analysis or premature termination of the study. The trial may be prematurely discontinued by the sponsor, chief investigator or regulatory authority on the basis of new safety information or for other reasons given by the regulatory authority or ethics committee.

10 Statistics

To determine a representative cut-off value for golimumab trough levels between the groups of patients stratified by disease activity/response a receiver-operator characteristics (ROC) curve will be created. A trade-off between sensitivity and specificity will be made to establish an adequate lower margin of the therapeutic golimumab range. This statistical plan was reviewed by an independent statistician at King's College London. Relationships between golimumab trough levels and patient characteristics and clinical parameters (albumin, serum CRP, formation of ADA's, fecal calprotectin and IBD-Control) will be evaluated.

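### Section 10.2 names only a t-test for responder comparisons, with no log scale, screening-value adjustment or test for proportions, so a real CRP or calprotectin difference may be missed

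*Combined protocol and SAP*

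**What the plan says.** Section 10.2 makes golimumab level the main variable and adds fifteen others. The list begins "Other variables will include: efficacy, gender, age, smoking status, concomitant medication, disease location, disease duration, development of anti-drug antibodies, acute infusion reactions" and ends "serum CRP, albumin, fecal calprotectin, SCCAI, PRO2, IBD-Control". The test sentence follows: "Differences between responders and non-responders will be evaluated using a t-test with the threshold for statistical significance set at 0.05". It does not say which variables it covers. The only other method in the section is "Univariate and bi-variate analysis will be used to assess factors predicting response, including serum golimumab levels at each time point", with no model, scale or covariates given.

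The opening paragraph of section 10 plans a separate evaluation of "Relationships between golimumab trough levels and patient characteristics and clinical parameters", including CRP and calprotectin, and also states no method.

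Section 6.1 admits cohort 1 patients with SCCAI above 5 plus any one of three signs of activity: calprotectin above 59 µg/g, "A raised CRP (> 5 mg/L) or" "Endoscopic disease activity Mayo 2 or above". Sections 4.3 and 7.1 schedule CRP and calprotectin at the cohort 1 screening visit and again at weeks 6, 10 and 14. Cohort 2 has one measurement of each. Response is defined by SCCAI alone (section 4.1.1). The two markers are secondary endpoints (4.1.2) and serve a tertiary objective (4.1).

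**The concern.** CRP and calprotectin are positive markers, usually with a long right tail (an assumption here; the protocol gives no distribution). A t-test on untransformed values compares arithmetic means, which a few very high results can dominate.

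Entry does not require either marker to be raised. A cohort 1 patient who starts with a normal CRP will probably have a normal CRP at week 14 whatever the drug does, and only the screening value can tell that patient from one whose CRP fell. The plan collects this value but gives it no role when the marker is the outcome.

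Six listed variables are categorical: gender, smoking status, concomitant medication, disease location (three levels in section 7.1), anti-drug antibodies and infusion reactions. A t-test does not suit these, and no alternative is named.

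Response rests on symptoms and section 4.3 schedules no follow-up endoscopy, so these markers are the main objective check on it. A null comparison could be read as showing that clinical response is unrelated to inflammation, when the method was weak.

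**Working it through.** **The plan's own figure.** Section 10.1 gives 42 patients per cohort for a 2 mg/L mean difference in serum concentration, 80% power, two-sided. Taking alpha as 0.05 and a 21:21 split, the implied SD is 2 / [(1.960 + 0.842) × √(1/21 + 1/21)] = 2 / (2.802 × 0.3086) = 2.31 mg/L. If 42 meant patients per group, it would be 3.27 mg/L. No SD is stated, so the 42 can be neither confirmed nor refuted. It concerns golimumab level and says nothing about power for CRP or calprotectin.

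**Inputs for the marker comparison.**
- From the plan: 42 patients in cohort 1; alpha 0.05.
- Assumed: a 21:21 split (section 3 puts primary non-response at about 50%); log-normal markers; natural-log SD 1.0–1.5; ratio of geometric means 2–3; correlation r of 0.3–0.5 between screening and follow-up log values.

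**Formulae.** For a t-test on the log scale, the non-centrality is ln(ratio)/SD × √(21/2), with 40 df. Adjusting for the screening value divides this by √(1 − r²), which is 0.954 at r = 0.3 and 0.866 at r = 0.5, with 39 df. The raw-scale test has no simple formula and was simulated.

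Non-centrality on the log scale:
- SD 1.0, ratio 2: 0.693 × 3.240 = 2.246
- SD 1.0, ratio 3: 1.099 × 3.240 = 3.560
- SD 1.25, ratio 3: 0.879 × 3.240 = 2.848
- SD 1.5, ratio 3: 0.732 × 3.240 = 2.373
- SD 1.5, ratio 2: 0.462 × 3.240 = 1.497

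**Power, all patients able to respond on the marker** (simulated; the log-scale columns agree with the formulae to within about 2 points):

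| log-SD | ratio | raw t-test | log t-test | log + screening, r = 0.3 | log + screening, r = 0.5 |
|---|---|---|---|---|---|
| 1.0 | 2 | 42% | 59% | 63% | 71% |
| 1.0 | 3 | 78% | 94% | 95% | 98% |
| 1.25 | 3 | 51% | 79% | 81% | 89% |
| 1.5 | 3 | 31% | 64% | 67% | 76% |
| 1.5 | 2 | 14–15% | 31% | 33% | 38% |

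The log scale adds about 16 to 33 points. The screening value then adds about 1 to 4 points at r = 0.3 and 4 to 12 at r = 0.5.

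**If 30% enter with that marker not raised and it does not fall** (assumed share; r = 0.3 and 0.6):
- SD 1.0, ratio 3: raw 48–54%, log 65–68%, log with screening value 68–82%.
- SD 1.5, ratio 3: raw 16–18%, log 37–38%, log with screening value 40–49%.

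**Where the gain is small.** At log-SD 0.8 with a 28:14 split, a 2-fold difference and 30% not raised, the raw test (43–46%) is no worse than the log t-test (39–44%). The log analysis with the screening value gives 45–56%. That adjusted analysis matched or beat the raw test in every scenario run.

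**The case against.** Four points on the other side have force.

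- **The t-test sentence names no variable.** A reader might infer that the plan prescribes a t-test for gender or disease location. It does not. Golimumab level is the stated main variable and the basis of the sample size, so the sentence may be meant chiefly for trough levels. Likewise, the plan never specifies the raw scale; it is silent on scale. This stands. What remains is that no other group test is named, so an analyst has nothing else to follow.
- **A real difference is not shown to be likely missed.** Spread, fold difference, correlation and split are all assumed. At log-SD 1.0 and a 3-fold difference the raw t-test has 78% power, and at log-SD 0.8 and 4-fold it reaches 99%. This stands too: the documents support a loss of power and a possible miss, no more.
- **The power figures do not address exposure against inflammation.** They compare responders with non-responders. The trough–marker evaluation in section 10 is separate and has no stated method, so no power can be attached to it. Its silence is itself a gap, as is that of the univariate and bi-variate analyses.
- **The screening value may be a weak covariate.** The screening visit can fall anywhere from day −90 to day 0, so the value may precede the week 6 sample by up to 42 + 90 = 132 days and the week 14 sample by up to 98 + 90 = 188 days. A low correlation is plausible, and at r = 0.3 the gain is only a few points. The case for the log scale does not depend on it.

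**Conclusion.** The point holds as a gap in specification with a real but uncertain cost in power. The only responder comparison named is a t-test, with no scale, no use of cohort 1 screening values and no method for categorical variables. Applied as written to right-skewed CRP or calprotectin, it gives up roughly 16 to 33 points of power against a log-scale t-test in the scenarios tabulated, and more against a baseline-adjusted one. Most of that gain comes from the log scale.

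The size rests on log-normal markers, log-SD 1.0–1.5, 2- to 3-fold differences and an even split, none of which the documents give. Baseline adjustment is possible in cohort 1 only: cohort 2 (70 of the 112 patients) has no screening value. A reader might infer that the trial's main result is at risk. It is not: the primary objective is a trough cut-off from a ROC curve with response defined by SCCAI, and neither marker enters it. This is worth correcting because it is cheap and fixes the method before the data are seen.

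**What to change.** In section 10.2, state the method by type of variable.

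- **CRP and calprotectin:** analyse on the log scale, both by response group and by linear regression on log trough. In cohort 1 include the marker's own screening value (log scale) as a covariate; in cohort 2 use the log scale only. State how values below the reporting limit enter the logarithm.
- **Categorical variables:** use Fisher's exact or chi-squared tests, with disease location kept as three categories.
- **Optional, supportive only:** repeat the cohort 1 marker analysis in patients raised at screening (CRP above 5 mg/L; calprotectin above 59 µg/g). If 30% are not raised, this leaves 42 × 0.7 = 29.4, or about 29 patients, so it should not replace the main analysis.

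The cost is SAP wording. Every value needed for the marker analyses is already scheduled, with no added visits or patients. Marker results would be reported as ratios of geometric means, which need a line of explanation for clinical readers.

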14.1 Source Data

Source data regarding eligibility review, demographic details, UC disease-related details, injection-site reactions and concomitant medication as well as clinical disease activity (SCCAI and PRO2) will be documented in the patients electronic notes. Data regarding biochemical disease activity will be printed from EPR and stored in a study specific folder along with quality of life questionnaires. Golimumab serum concentrations and anti-drug antibody measurements will also be stored in the study specific folder.

15 Data Management

Anonymised patient data will be recorded on a bespoke password protected electronic CRF created by King's Clinical Trials Unit. All patient specific data will be recorded using only this number. The full name and birth date will only be recorded on the informed consent form. The study coordinator will monitor patient inclusion and protocol steps, coordinate data entry, perform data analyses and reporting.

16 Publication Policy

Patients are entitled to public disclosure of the results of the trial on the basis of their participation in it. The results of research will be submitted for publication to peer-reviewed scientific journals. Data generated during this study would be of interest and appropriate for publication in the IBD section of high impact general gastroenterology journal (e.g. Gastroenterology, Gut or Clinical Gastroenterology & Hepatology), a specialist IBD journal (Inflammatory Bowel Diseases, The Journal of Crohn's and Colitis) or a specialist Gastroenterology therapeutics journal (Alimentary Pharmacology & Therapeutics). Data in abstract form would be submitted to meetings such as ECCO, BSG, DDW and UEGW.

17 Insurance / Indemnity

No trial-specific insurance/indemnity is in place. Standard NHS insurance/indemnity will apply.

18 Financial Aspects

Funding to conduct the trial is provided in the form of an initial £81,683 grant from Merck Sharp & Dohme (MSD) with a further £15,547 following the increase in recruitment target.

19 Signatures

